4. DEVICE DESCRIPTION

4.1 DESIGN

The Gebauer[™] Lenticule is a corneal Implant made of highly purified, transparent collagen of animal origin. The Gebauer[™] Lenticules undergo a complex manufacturing process followed by a validated terminal UV-sterilization step. The result is a co-planar implant which is free of cells and their remnants.

Figure 1: The Gebauer™ Lenticule implant - Example

4.2 DEVICE PRINCIPLE OF OPERATION

The Gebauer[™] Lenticule represents a corneal stromal implant device which is intended to be implanted in a patient's cornea in order to change its thickness and/or to change the cornea's anterior curvature and/or to replace defective, compromised or vacant stromal tissue.

The Roval	Document No.	Version	Document Date	Author	Page: 19
Wolverhampton NHS Trust	CIP Study No. 2019OPH108	1.6	03 August 2021	[name]	Out of: 60

4.3 INTENDED USE

The Gebauer[™] Lenticule is intended for ophthalmic lenticular intrastromal keratoplasty (or keratophakia). Thereby it is intended to be implanted in a patient's cornea in order to change its thickness and/or to change the cornea's anterior curvature and/or to replace defective, compromised or vacant stromal tissue. Based upon this intended purpose, the various Gebauer[™] Lenticule geometries can be used for the following clinical conditions/indications:

- 1) Co-planar lenticules of variable thicknesses and diameters: E.g. for the treatment of keratoconus or post-LASIK Ectasia.
- 2) Curved lenticules of different diameters and variable spherical and astigmatic geometries: E.g., for the treatment of ametropia / refractive errors.

Based upon these general therapeutic fields, the current clinical study is intended to investigate the effectiveness and safety of Gebauer[™] Lenticules in the treatment of patients suffering from either severe keratoconus or post-LASIK Ectasia.

5. STUDY OBJECTIVES AND ENDPOINTS

5.1 OBJECTIVES

The objective of this study is to evaluate the safety and indicative effectiveness of Gebauer[™] Lenticule when implanted in subjects suffering from keratoconus or post-LASIK ectasia. Therefore, numerous clinical endpoints have been identified, based upon scientific literature, to investigate both safety and effectiveness aspects of the GebauerTM Lenticules (see below Chapter 5.2).

5.2 CLINICAL ENDPOINTS

5.2.1 PRIMARY SAFETY ENDPOINTS

The following primary safety endpoints have been determined and will be systematically documented in the Case Report Form for each patient visit:

- Signs of immunological rejection during the post implantation observation period
- The frequency and severity of all treatment-related adverse events, during implantation of the Gebauer™ Lenticule and throughout the post implantation observation period.

The Royal	Document No.	Version	Document Date	Author	Page: 20
Wolverhampton NHS Trust	CIP Study No. 2019OPH108	1.6	03 August 2021	[name]	Out of: 60

5.2.2 SECONDARY SAFETY ENDPOINTS

The following secondary safety endpoints have been determined and will be systematically documented in the Case Report Form for each patient visit:

- Changes in IOP during observation period
- Changes in corneal transparency and lenticule transparency during observation period
- Inflammation of cornea or sclera during observation period
- Changes to the corneal epithelium during observation period
- Changes to conjunctiva, iris/pupil, lens during observation period
- Changes to ocular pain/discomfort during observation period

5.2.3 PRIMARY ENDPOINTS FOR EFFECTIVENESS

The following primary endpoints for effectiveness have been determined and will be systematically documented in the Case Report Form for each patient visit:

- Changes in corneal topography (central K-reading results): at baseline vs. post implantation observation period
- Changes in central corneal thickness at baseline vs. post implantation corneal thickness (cornea plus lenticule)
- Patient satisfaction with received treatments and outcome

5.2.4 SECONDARY ENDPOINTS FOR EFFECTIVENESS

The following secondary endpoints for effectiveness have been determined and will be systematically documented in the Case Report Form for each patient visit:

- Best corrected visual acuity during the observation period
- Investigator's overall procedure evaluation
- Suitability of pocket size
- Duration of surgical procedure
- Requirement of specific post surgical measures (suturing after implantation, bandage contact lens, antibiotic and immunosuppressive treatments)

The Royal	Document No.	Version	Document Date	Author	Page: 21
Wolverhampton NHS Trust	CIP Study No. 2019OPH108	1.6	03 August 2021	[name]	Out of: 60

6. STUDY DESIGN AND STUDY DURATION

This investigator-initiated clinical research study is an open-label, single site clinical investigation, which follows the Good Clinical Practice guidelines as described in EN ISO 14155.

The primary aim of this study is to assess the safety and effectiveness of the Gebauer[™] Lenticules after corneal implantation in patients suffering from severe keratoconus or post-LASIK ectasia. Specific clinical endpoints, as documented in Chapter 5.2 above, have been identified in order to systematically investigate and document particularly relevant aspects of clinical safety and effectiveness of this innovative treatment option.

Subjects with severe keratoconus or post-LASIK ectasia are eligible for this study. Only subjects who have signed the informed consent form and meet all the eligibility criteria listed in Chapter 7.1 and 7.2 below will be qualified for enrollment. The study will encompass a total of 15 subjects who will complete the follow-up schedule as described in this Clinical Investigation Plan.

In summary, as listed in Chapter 8.7.5, after patients were enrolled in the study, a detailed ophthalmological examination is performed, in order to document the current status of both patient eyes (Baseline Day -30 – Day -1). On Day 0, a flap is created in the eye at the Optimax clinic, then on Day 0 (+ 30 days) patients are implanted with the GebauerTM Lenticule on 1 diseased eye. The untreated eye serves as a reference during the complete observation period.

After implantation, subjects will be followed up frequently for a period of 6 months with ophthalmic assessments at day 1-3; 28 days (+/- 7days), 3 months (+/- 14 days) and 6 months (+/- 28 days). In addition 2 weekly, telephone assessments will be conducted up to 3 months. After this period, the primary clinical investigation report will be issued.

In addition to that, two further optional patient visits are planned to investigate long-term safety and effectiveness of the Gebauer[™] Lenticules. Therefore, 1 and 2 years post implantation, patients will be invited to come back to the hospital for additional ophthalmic examinations. The results of these long-term follow-up visits will be in separate addendum reports, independently from the basic clinical investigation report.

For this clinical investigation, the following time frame is anticipated: Completion of active enrolment is expected to require approximately 1-3 months. The primary endpoints will be achieved when the last study subject has completed his/her 6 months follow-up. For the assessment of long-term tolerability, subjects will be invited to additional follow-up visits after 1 and 2 years. Therefore, the total duration of the study is expected to be 9 months (for completion of the 6 months follow-up period), respectively, 27 months (for completion of the 2 years follow-up period).

The Royal	Document No.	Version	Document Date	Author	Page: 22
Wolverhampton NHS Trust	CIP Study No. 2019OPH108	1.6	03 August 2021	[name]	Out of: 60

7. STUDY POPULATION

Men and women aged 18 or over and less than 80 years old, suffering from keratoconus or post-LASIK ectasia, who meet the inclusion/ exclusion criteria and provided written Informed Consent will be enrolled in the study.

7.1 INCLUSION CRITERIA

Candidates for participation in the study must meet all of the following inclusion criteria:

- Diagnosis of severe keratoconus in patients who would prefer to avoid corneal transplant surgery / penetrating keratoplasty
 OR
- Diagnosis of severe post-LASIK Ectasia in patients who would prefer to avoid corneal transplant surgery / penetrating keratoplasty
- In terms of general health, patients must be free of diagnosed terminal illnesses (life expectancy of ≥ 2 years).
- Patients must be aged 18 years or over and less than 80 years old
- Patients' contact lenses must have been removed at least one-week prior to surgery for soft lenses and two weeks prior to surgery for hard lenses
- Subject understands the study requirements and the treatment procedures and provides written Informed Consent before any study-specific tests or procedures are performed
- Patient must be able and willing to complete all study visits and comply with the studyspecific requirements

7.2 EXCLUSION CRITERIA

Candidates for participation will be ineligible for the study if any of the following conditions apply:

- History or presence of any ocular pathologies that may interfere with the planned surgical treatment, including corneal epithelial problems
- Previous corneal transplantation or corneal implant in the designated eye
- Cataract with anticipated surgical intervention (IOL implantation) within 2 years
- Active inflammation and/or infection of the eye or the eye lid
- Patients with IOP <10 mmHg or >21 mmHg
- Professionally diagnosed and currently treated autoimmune diseases
- Current strong symptoms of any allergy
- History of major organ transplantation and/or current continuing immunosuppressive treatment
- History of blood transfusion within the last 12 months

The Royal	Document No.	Version	Document Date	Author	Page: 23
Wolverhampton NHS Trust	CIP Study No. 2019OPH108	1.6	03 August 2021	[name]	Out of: 60

• Subject who is currently participating or has participated in another investigational clinical study within the past 60 daysPregnancy and lactation

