Based upon the study results obtained in this GC/MS and ICP-OES investigation, and considering the fact that the investigational Gebauer[™] Lenticules only consists of purified porcine collagen fibers, the manufacturer Gebauer Medizintechnik GmbH decided that animal experimental tests for irritation, systemic toxicity, material-mediated pyrogenicity, and additional tests for genotoxicity can be waived both in view of scientific considerations relating to the known biocompatibility of porcine collagen and in view of the current animal protection regulations as described in EN ISO 10993-2.

Conclusion: As documented in a formal "Declaration of Compliance" / "Overall Biological Risk Assessment" as requested in EN ISO 10993-1 Chapter 7, and based upon both experimental study results and evaluation arguments, and considering the provisions of the current version of the harmonized standard EN ISO 10993-1 as well as FDA Guidance "Use of International Standard ISO 10993, 'Biological Evaluation of Medical Devices Part 1: Evaluation and Testing within a Risk Management Process", dated 16. June 2016, it is concluded that the investigational Gebauer™ Lenticules can be evaluated biocompatible if manufactured appropriately and applied in compliance with their intended use as outlined in the manufacturer's Technical Documentation and in this Clinical Investigation Plan.

The Roval	Document No.	Version	Document Date	Author	Page: 18
Wolverhampton NHS Trust	CIP Study No. 2019OPH108	1.6	03 August 2021	[name]	Out of: 60

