15.2 SERIOUS ADVERSE EVENTS (SAE)

An AE should be classified as an SAE and reported as such, if it meets one or more of the following criteria:

- It results in death (i.e., the AE actually causes or leads to death)
- It is life threatening (i.e., the AE places the subject at immediate risk of death)
- It requires or prolongs inpatient hospitalization
- It results in persistent or significant disability/incapacity (i.e., the AE results in substantial disruption of the subject's ability to conduct normal life functions)
- It results in a congenital anomaly/birth defect in a neonate/infant born to a mother exposed to the investigational product
- It is considered a significant medical event by the investigator based on medical judgment (e.g., may jeopardize the subject or may require medical/surgical intervention to prevent one of the outcomes listed above)
- It is considered sight-threatening by the investigator

If a subject is hospitalized to undergo a medical or surgical procedure as a result of an AE, the event responsible for the procedure, not the procedure itself, should be recorded as the event. For example, if a subject is hospitalized to undergo coronary bypass surgery, record the heart condition that necessitated the bypass.

The Royal	Document No.	Version	Document Date	Author	Page: 42
Wolverhampton NHS Trust	CIP Study No. 2019OPH108	1.6	03 August 2021	[name]	Out of: 60

Hospitalizations for the following reasons will not be recorded as SAEs:

- Hospitalization or prolonged hospitalization for diagnostic or elective surgical procedures for preexisting conditions
- Hospitalization or prolonged hospitalization required to allow outcome measurement for the study
- Hospitalization or prolonged hospitalization for scheduled therapy of the target disease of the study.
- Clinical events to be considered and reported as SAE's include (but are not limited to):
- Infectious keratitis
- Serious allergic reaction

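### The allergy exclusion depends only on current symptoms, so a known but symptom-free porcine or collagen hypersensitivity is eligible for a porcine collagen implant; the autoimmune wording also needs reconciling or justifying

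*Protocol*

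**What the plan says.** Section 7.2 of the protocol, repeated in the synopsis, has several exclusions that bear on immune risk:

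- "Current strong symptoms of any allergy"
- "Professionally diagnosed and currently treated autoimmune diseases"
- "History of major organ transplantation and/or current continuing immunosuppressive treatment"
- "History of blood transfusion within the last 12 months"
- "Previous corneal transplantation or corneal implant in the designated eye"

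The device is a disc of purified porcine collagen (section 2.2). The first of the two primary safety endpoints in 5.2.1 is "Signs of immunological rejection during the post implantation observation period"; the second is treatment-related adverse events. Sections 13.7.5 and 15 also treat rejection as primary, whereas the synopsis lists only treatment-related adverse events. Section 14.2 names device rejection among the risks, and section 15.2 gives "Serious allergic reaction" as an example of an event to be reported as an SAE.

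On screening, 8.5.1 and the schedule in 8.5.9 list an ophthalmic medical history, and 8.5.1 adds medication use. Section 8.4 says that everyone who meets the eligibility requirements will be invited.

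**The concern.** An allergy to a material usually produces symptoms only on exposure. A criterion that looks only at symptoms on the day can exclude someone with strong hay fever and admit someone with a documented reaction to porcine material or collagen who is not currently exposed. For an implant made of that material, the second patient is the more relevant one.

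The autoimmune criterion has a related feature. It requires a diagnosis and current treatment together, so a patient with the same diagnosis who is off treatment does not meet it.

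Two things are at stake: the safety of a patient whose history could have been asked about, and the reading of a primary safety endpoint in 15 subjects. If one rejection or allergic event occurred in someone with a known hypersensitivity to the material, the report could not say how much was due to the device and how much to a host factor that screening could have identified.

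**Working it through.** There is no figure in the plan to reproduce: section 13.3 states that no formal sample size calculation was done. The check is a literal reading of the criteria, with a short calculation for scale.

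**Step 1. What triggers each immune-related exclusion in 7.2?**

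- Allergy: current strong symptoms. No look-back and no named material.
- Autoimmune disease: a diagnosis and current treatment, both required.
- Immunosuppressive treatment: current.
- Major organ transplantation: history.
- Blood transfusion: history, 12 months.
- Corneal graft or implant: history, designated eye.

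The dependence on current status is therefore confined to the allergy criterion, the autoimmune criterion and the immunosuppression half of the third item. The other three look back.

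**Step 2. Does another criterion catch these patients?** A symptom-free hypersensitivity to porcine material or collagen meets none of the exclusions in 7.2, and nothing in 7.1 bars it. Untreated autoimmune disease is caught only if it involves the eye, through the ocular-pathology or active-inflammation items.

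**Step 3. Would it come to light?** Medication use can reveal treated disease. It does not reveal a dormant allergy or an untreated condition, and no listed baseline item asks about either.

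**Step 4. Scale of one event.** Exact (Clopper-Pearson) 95% intervals, n = 15 (section 13.3):

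- 0 events: the upper limit is 1 − 0.025^(1/15) = 0.218, so the interval is 0 to 21.8%.
- 1 event: 1/15 = 6.7%. The lower limit is 1 − 0.975^(1/15) = 0.0017 and the upper limit is the 97.5% point of Beta(2, 14) = 0.319, so the interval is 0.2% to 31.9%.

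One event raises the upper limit by 31.9 − 21.8 = 10.1 percentage points.

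**Step 5. Illustration for the autoimmune criterion.** The documents give no prevalence of diagnosed, untreated autoimmune disease. For an assumed prevalence p, the chance of at least one such patient among 15 is 1 − (1 − p)^15:

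- p = 1%: 14%
- p = 2%: 1 − 0.98^15 = 26%
- p = 5%: 1 − 0.95^15 = 54%
- p = 10%: 79%

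The spread shows that the assumption drives the result. These are chances of enrolling such a patient, not of a rejection. No corresponding figure is offered for porcine or collagen hypersensitivity, for which the documents give no basis.

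**The case against.** The strongest reply is that the written criteria are not the only control. The Chief Investigator must approve the screening results (8.4), and a consented patient may still be excluded on medical examination (8.2). Section 8.1 mentions history among the pre-procedure assessments, and section 20 requires a medical history sufficient to verify the entry criteria. After implantation, symptoms of immune activation are an indication for removal (section 9), and the procedure is described as reversible (2.2). These points stand as general safeguards. They do not close the material-allergy gap: none states an allergy rule, and a history kept to verify the entry criteria need not cover something those criteria never mention. Removal acts only after the event.

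The reply is stronger on autoimmune disease. A reader might infer that untreated patients are those most likely to reject the implant and so must be excluded. The documents do not support that. Untreated disease may be inactive, and no section reports rejection risk by autoimmune status. The one relevant statement, in 14.1, is that an implant free of foreign cellular components should carry a much lower rejection risk than donor tissue. That is a comparison with grafts and is not offered as a reason for the narrow criterion, but nothing in the text contradicts it. Nor is the requirement of current treatment redundant beside the immunosuppression criterion, since autoimmune disease can be treated without immunosuppressants.

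A reader might also lean on section 3, where the manufacturer decided that "animal experimental tests for irritation, systemic toxicity, material-mediated pyrogenicity, and additional tests for genotoxicity can be waived". None of the tests listed there is named as a sensitisation or rejection test, and the assessment also drew on literature, so the waiver does not show that hypersensitivity was left unassessed. Likewise, the SAE example of a serious allergic reaction is not tied to the implant material.

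Finally, the study is mainly descriptive (13.3, 13.7.1) and sets no success threshold, so moving from 0/15 to 1/15 crosses no decision rule, and the two intervals overlap heavily.

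**Conclusion.** The allergy point holds on the text alone and needs no prevalence assumption: as written, known hypersensitivity to the implant's own material is not an exclusion unless strong symptoms are present at the time. Its expected effect on the results cannot be quantified from the documents; the single-event shift shows only how sensitive a 15-patient safety summary is.

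The autoimmune point holds in a narrower form. Diagnosed but untreated disease is admitted, and the protocol does not explain why treatment status should decide eligibility when rejection is a primary safety endpoint. That calls for reconciliation or justification; whether such patients should be enrolled is a clinical judgement that the documents do not settle.

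Two broader readings should be avoided. It is not true that all the immune-related exclusions depend on current status, because the transplantation, transfusion and prior-graft items are history-based. Nor is rejection the sole primary safety endpoint. The 26% to 54% range for prevalences of 2% to 5% is illustrative only and says nothing about harm.

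**What to change.** 1. In section 7.2 and the synopsis, keep the current-symptom criterion and add a separate exclusion: known hypersensitivity to porcine-derived material or collagen.
2. In 8.5.1, with the matching row in 8.5.9 and the baseline case report form, add a history question on this item so that the criterion can be verified.
3. For autoimmune disease, have the sponsor either reconcile the requirement of current treatment with the rejection endpoint or state why diagnosed but untreated disease is deliberately admitted. No particular rule is proposed here.

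Items 1 and 2 cost one line in each of two places and one history question, with no extra test or visit; the downside is at most a rare additional screen failure. Item 3 costs a sentence of justification or a wording change, as the sponsor decides.

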8. STUDY PROCEDURES

8.1 SUBJECT SCREENING

Subjects will be selected from the physician's usual patients practice. All subjects meeting the inclusion/exclusion criteria and having signed the Informed Consent Form will be evaluated by the Investigator according to the study protocol.

Any pre-procedure assessment or tests that are required before entering subjects to the study (history and ophthalmic examinations, laboratory tests) will be analyzed and interpreted at the study site.

A screening log will be maintained by the site for all the subjects screened. This list includes both enrolled and non-enrolled patients.

Every effort will be made to correctly establish eligibility of the participants prior to enrolment. Subjects who do not meet all inclusion/exclusion criteria as listed in Chapter 7.1 and 7.2 will not be enrolled in the study.

Where the participant's first language is not English, the Site's interpreting services will be utilised as per Site's standard protocols.

8.2 INFORMED CONSENT PROCEDURE

The background and purpose of the proposed study and its potential risks and benefits will be explained to the subject under the care of the Investigator. The subjects must be informed about their right to withdraw from the Study at any time and for any reason without sanctions, regulatory consequences, or loss of benefits to which the subject is otherwise entitled, and that withdrawal from the study will not jeopardize their future medical care.

Written Informed Consent must be obtained for all subjects who are potential study candidates before any study-specific tests or procedures are performed. Subjects who meet general entry criteria will be asked to sign the study-specific Informed Consent Form, which has previously been approved by an Ethics Committee (EC). Before signing, the responsible doctor will explain the details of the planned clinical investigation and will inform about potential alternative treatments. Furthermore, the responsible doctor will explain that a patient might be excluded from participating in the study, irrespective of signing the informed consent form, based upon medical examination.

